needs and circumstances of midlife and older Latinos living with HIV. HOLA builds on prior research using health promotion to prevent depression and anxiety in older Latinos. In the present context, HOLA uses a lay community health worker (CHW) to lead a health promotion program in order to reduce cardiometabolic risk and improve psychosocial functioning and health-related quality of life in midlife and older Latinos living with HIV. Such an approach could appeal to midlife and older Latinos living with HIV as a nonstigmatizing and culturally acceptable intervention. HOLA addresses multiple concerns that are prevalent in this community (cardiometabolic risk, psychological distress). In addition, cultural values and beliefs were included in the formative and development phases of the intervention to ensure that the different socio-cultural influences that have a role in the health of Latinos were incorporated. Thus, HOLA is the optimal choice to address an urgent medical and public health issue, and one that is rapidly growing. The objectives of this pilot study are two-fold: (1) to evaluate the feasibility and acceptability of HOLA among HIV-infected Latinos aged 50 and older and (2) identify modifications needed in the design of a larger, ensuing hypothesis testing study. HOLA, which is informed by Behavioral Activation and Social Learning theory is a CHW-led, multicomponent, health promotion intervention consisting of: (1) a social and physical activation session; (2) a moderately intense group walk led by a CHW for 45 minutes, 3x/week for 16 weeks; (3) pleasant events scheduling. The proposed pilot study will recruit and enroll 18 community dwelling Latinos living with HIV aged 50+. Participants will be assessed at three time points (baseline, post intervention, and 3 months post intervention) on measures of cardiometabolic risk factors (waist circumference, dyslipidemia, hypertension, and glucose), psychosocial functioning, and health-related quality of life. Consistent with recommendations from biostatistical workgroups funded by NIH, this pilot study is not powered to test a hypothesis. Rather, this pilot study is a requisite initial step in exploring an innovative application of the HOLA health promotion intervention.

5) **Inclusion and Exclusion Criteria***

Inclusion Criteria:

The following conditions must be met for study eligibility:

- are Latino (self-identified);
- are age 50+;
- are male;

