This study will not include women in that the specific research questions are targeted toward males. This study will specifically target Latinos. Individuals from other ethnic backgrounds are excluded as the study intervention is specifically tailored to address and target the specific needs and preferences of older Latinos with risk of cardiometabolic disease. This study is specific to only Latino males and will only report data on Latino males; findings from the study are intended to only be generalizable to Latino males. Both Black and White Latino males will be included in the study. We are not powered to detect differences between racial groups of Latino men. Previous research indicates that the outcomes in this study along with engagement with the intervention suggests no differences between racial groups of Latino males; no significant differences have been found in any outcomes in HOLA pilot data. We will use respondent self-report or self-identification to collect data on ethnicity and race. Though this application talks of racial/ethnic disparities and refers to Latino as an ethnicity, we are aware of the limitations of this construct. We acknowledge that ethnicity is a social construct and that Latinos are not a homogeneous, monolithic group even though the U.S. Census definition classifies them into one uniform ethnicity. Also, many racial/ethnic differences that have been identified in previous research are in fact confounded by socioeconomic status (SES). However, even though SES is indeed a central determinant of health status and overlaps with the concept of race, SES does not account for all racial health disparities.

6) **Number of Subjects***

18 older Latinos age 50+ will be enrolled.

7) **Study-Wide Recruitment Methods***

Recruitment procedures will protect participant confidentiality.

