In addition, we will also collaborate with another study, the Clinic Registry Project (IRB#20160911), which serves as a consent to contact database, to contact eligible participants. They will provide us with contact information for participants in their study who have consented to be contacted by other studies. When contacting participants, the CHW will follow the phone script for calling UHealth consent to contact participants that has been tailored to this study.

8) **Procedures Involved***

Participants will be assessed at three time points (before starting the study, 4, and 7 months after the first interview) on measures of cardiometabolic risk factors (waist circumference, dyslipidemia, hypertension, and glucose), psychosocial functioning, and health-related quality of life.

All participants will read and sign an informed consent document and a HIPAA Research Authorization – Form B approved by the University of Miami Institutional Review Board (IRB). They will initially be provided with a verbal summary of the study and for those who appear to have problems reading the consent form it will be read aloud. Participant payments will be graduated. Participants will receive \$15 on the first visit, \$25 on the second visit, and \$35 on the third visit (total of honoraria = \$75).

Prior to starting the baseline assessments, blood draws will take place at the UM/JMMC Adult HIV Outpatient Clinic. Study staff will obtain initial HDL-C, LDL-C, triglycerides, insulin, and HbA1c levels via review of the electronic medical records. Trained and certified research assistants (RAs) who have at least a bachelor's degree will conduct all assessments in private offices at the UM/JMMC Adult Outpatient HIV Clinic, at a private interview room at the CTRS located on the 7th floor of the Don Soffer Clinical Research Center, or the participant's home. To ensure privacy in the home, we will conduct the interview in a private room with a door of the participant's choosing away from any common areas. In the event that there are other people in the house, the door can be closed to maintain privacy. In the event that an in-person interview is not feasible then the interview will be

IRB Study Number: 20181032

Version 8, Date: 07/16/2021

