conducted over the telephone. At 4 and 7 months after the initial interview, fasting blood samples will be drawn via venipuncture and stored at 4°C until analysis. HOMA will be calculated, providing a measure of insulin resistance. Study measures will be administered after the blood draws.

Assessment Measures

Cardiometabolic Risk: list of current medications, waist circumference, total cholesterol, HDL-C, LDL-C, triglycerides, blood pressure, and HbA1c, will be used to measure cardiometabolic risk.

Dementia Screen: The Mini Mental Status Exam (MMSE) will be used to screen for dementia. A Mungas-adjusted score of 23 or below indicates cognitive impairment.

Walking Ability: The 10 meter walk test will be used to evaluate walking ability, which has been used as a screening instrument to measure functional mobility and gait speed in physical activity interventions with older adults.

Demographics: The CLaRO Demographics Form will be used to collect demographic information (e.g., gender, education, income, preferred language, country of origin, time in the US, etc.) and will include a list of all diagnosed medical conditions and medications.

Acculturation: The 24-item Bidimensional Acculturation Scale (BAS) will be used to measure acculturation.

Depression Severity: The 20-item Center for Epidemiologic Studies Depression (CES-D) Scale and the 9-item Patient Health Questionnaire (PHQ-9) will be used to measure depression severity.

Anxiety Severity: The 7-item Generalized Anxiety Disorder (GAD-7) scale and the 14-item Perceived Stress Scale will be used to measure anxiety severity.

Social Support: Perceived social support will be measured using the 12-item Multidimensional Scale of Perceived Social Support (MSPSS).

Health Related Quality of Life: The SF-12 will be used to assess for health related quality of life.

Physical Activity: The 16-item Global Physical Activity Questionnaire (GPAQ) will be used to measure physical activity.

Stigma: The HIV Stigma Scale (HSS) is a 40 item measure of stigma and psychosocial aspects of having HIV.

IRB Study Number: 20181032

Version 8, Date: 07/16/2021

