Project Evaluation: we will use a project evaluation questionnaire developed by investigators at the CNSA and used in previous studies. The items are a mix of rating scales, yes/no questions, and open-ended questions that allow participants to give feedback in short answer format with specific interest in understanding the participants' opinions regarding the specific components of the intervention.

After the baseline assessment, participants will be enrolled into the HOLA intervention.

Intervention Description: Content and Structure of HOLA

HOLA is a 16-week multi-component, health promotion intervention for older Latinos with subthreshold depression or anxiety. Aside from the maintenance phase (described below), the length and content of the intervention remain unchanged from the pilot study.

The first component of HOLA consists of two manualized social and physical activation sessions. Prior to beginning the group walk phase, each participant will meet individually with a CHW for the physical and social activation session. This session will last 30 minutes. The purpose of this session is to (a) educate potential participants about the goals of the intervention; (b) to motivate participants to engage in physical activity; (c) to increase participants' social activities (d) identify potential obstacles that may interfere with meeting the demands of the intervention; and (e) to brainstorm ways to overcome these obstacles. Participants will meet individually with the CHW for 30 minutes during week 8 to discuss progress of physical and social activity goals. These meetings will be held in the participants' homes.

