The second component is a group walk, led by a CHW for 45 minutes, 3 times a week. The group walk protocol uses the concept of interval training. An interval program requires that the work phase be higher intensity than the active recovery phase. The program starts slowly and gradually increases in workload by manipulating three factors: (a) intensity: governed by speed; (b) volume: duration and/or distance; and (c) work/recovery cycle: how long work phase lasts compared to the recovery phase. The intensity of the workout will be governed by the participants own perceived effort. The subject should learn to "feel" three intensity levels: low, medium and high. Low intensity can be defined as walking at a level that is equivalent to walking through a mall while easily having a conversation with a friend. Moderate intensity is when the subject notices his/her breathing increasing to slight discomfort, and he or she is walking at a good pace. High intensity is walking at a speed where the participant is short of breath and can't maintain the pace. Our decision to use walking as the exercise mode for activation is scientifically sound since no mode or location of aerobic exercise appears to be superior to another. Walks will be conducted with a group of six participants. Each walk will begin with 10 minutes of stretching and warm up. Then, participants will walk for 30 minutes. The walk will conclude with 5 minutes of cool down. The

IRB Study Number: 20181032

Version 8, Date: 07/16/2021

groups will be mixed gender and will include bilingual and monolingual Spanish speaking participants.

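### Follow-up visits are timed from each man's first interview, so the post-intervention visit falls before week 16 of the walks if he waits more than about 1.4 weeks to start

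*Combined protocol and SAP*

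**What the plan says.** The combined protocol and SAP uses two reference points for the same visits.

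- **Intervention clock.** Section 4 (Background) lists the assessments as "baseline, post intervention, and 3 months post intervention". Section 10 (Data Management) follows this: retention is judged on the assessment after the intervention, and the Aim 3 change runs from baseline to that assessment.
- **Interview clock.** Section 8 (Procedures Involved) places the assessments "before starting the study, 4, and 7 months after the first interview" and repeats this for the laboratory work: "At 4 and 7 months after the initial interview, fasting blood samples will be drawn via venipuncture".

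The steps before the first walk are these:

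- Section 7 has clinic staff introduce men individually at routine care visits, with a contact registry as a second route.
- Section 8 states: "After the baseline assessment, participants will be enrolled into the HOLA intervention". An individual session with the community health worker then precedes the walks.
- Walks run "for 45 minutes, 3x/week for 16 weeks" (Section 4), and "Walks will be conducted with a group of six participants" (Section 8). With 18 men (Section 6), that is three groups.

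The document gives no maximum interval from baseline to first walk and no visit window. It does not say whether a group may start with fewer than six men or admit men later.

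**The concern.** A site scheduling from Section 8 would count from each man's interview, whereas the analysis in Section 10 assumes that visit 2 follows the intervention. If the first walk comes late, three things follow.

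1. **Aim 3.** Visit 2 would measure an incomplete programme, by an amount that differs between men according to how long each waited. The repeated measures ANOVA treats the visit as one common time point. Its listed covariates (age, socioeconomic status, education and medication changes) do not include weeks of HOLA received.
2. **Aim 1 retention.** A man could be counted as retained while still in the programme, and a dropout after that visit but before week 16 would be missed. The threshold is 85% of 18, which is 15.3 and so 16 men; misclassifying a few men could change the result.
3. **Visit 3.** It would come less than three months after the last walk, before the three-month booster phase has ended.

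**Working it through.** **Inputs**

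- Visits 2 and 3: 4 and 7 months after the first interview (Section 8). I take the first interview to be the baseline interview.
- Walks: 3 per week for 16 weeks (Section 4), so 3 × 16 = 48.
- One month: 365.25 / 12 / 7 = 4.348 weeks. Four-week months are used as a variant.
- Wait *w*, in weeks, from first interview to first walk: not stated. It is an assumption, shown over a range.

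**Step 1. Reproduce the plan's schedule.** With *w* = 0 the walks end at week 16, and three months later is 16 + 3 × 4.348 = 29.04 weeks. The stated visits fall at 4 × 4.348 = 17.39 and 7 × 4.348 = 30.44 weeks. With four-week months the stated visits are at 16 and 28 weeks, exactly the end of the walks and three months later. The two schedules therefore match if walking starts at once.

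**Step 2. Slack.** 17.39 − 16 = 1.39 weeks. With four-week months it is 16 − 16 = 0.

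**Step 3. Effect of a wait.**

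- Weeks of walks offered by visit 2 = min(16, max(0, 17.39 − *w*)); walks = 3 × that.
- Weeks from last walk to visit 3 = 30.44 − 16 − *w* = 14.44 − *w*. The intended gap is 3 × 4.348 = 13.04.

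| Wait (weeks) | Weeks of walks by visit 2 | Walks, of 48 | Weeks from last walk to visit 3 |
|---|---|---|---|
| 0 | 16.0 | 48 | 14.4 |
| 1.39 | 16.0 | 48 | 13.0 |
| 2 | 15.4 | 46 | 12.4 |
| 4 | 13.4 | 40 | 10.4 |
| 8 | 9.4 | 28 | 6.4 |
| 12 | 5.4 | 16 | 2.4 |

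With four-week months, waits of 4 and 8 weeks give 36 and 24 walks by visit 2. Visit 3 then falls 8 and 4 weeks after the last walk, against 12 intended.

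**Step 4. Threshold for no walks at all by visit 2.** 17.39 − *w* ≤ 0 requires *w* of about 17.4 weeks or more.

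**Step 5. Intervention clock.** If visit 2 follows the week-16 walk and visit 3 comes three months later, every man has been offered 48 of 48 walks by visit 2 and the gap to visit 3 is about 13.0 weeks, whatever the wait.

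**The case against.** The strongest reply is that Section 8 simply restates the Background in calendar terms: 16 weeks is nominally four months, and four plus three is seven. That is right as far as it goes, and Step 1 confirms it. The two clocks part only when there is a wait, and no wait is written into the plan.

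A reader might infer that the first men in each group must wait until six have been interviewed. The document does not say so. Section 7 describes introduction and consent at the clinic visit, not the baseline interview, so men could be consented one by one and interviewed when a group is ready. Section 11 speaks of baseline procedures in a first wave of participants, which may mean batched baselines. Intensity is set by each man's own perceived effort, so staggered entry is not excluded either.

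A reader might also infer that some men would have visit 2 before their first walk. That needs a wait of about 17.4 weeks or more. If a group started only when full, the first man would wait for five more; at 1.25 men per month that is 5 / 1.25 = 4 months. Neither the accrual rate nor the start rule is stated, so this is an extreme case and not a finding.

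Finally, the 80% session-attendance criterion records exposure separately, so a partial dose would not go wholly unseen. But it does not move visit 2 or enter the Aim 3 model.

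What remains is a schedule with 1.4 weeks of slack at most, several steps to complete before walking starts, and no cap on the interval.

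**Conclusion.** The point holds in conditional form. The interview clock and the intervention clock agree only if walking starts within about 1.4 weeks of the first interview, or immediately if months are counted as four weeks. Any longer wait puts the post-intervention visit inside the programme and brings visit 3 closer than three months to the last walk. At a 4-week wait the shortfall at visit 2 is about 8 of 48 walks (48 − 40); at 8 weeks it is about 20 (48 − 28).

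These figures depend on the assumed wait alone. Whether waits of that length occur, and for how many men, cannot be determined from the document.

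Severity is should-fix. This is an 18-man, single-arm pilot that is stated not to be powered, and Aim 3 is exploratory. No sample-size figure changes. One of the Aim 1 feasibility criteria, retention, does rest on visit 2.

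**What to change.** In both places in Section 8 where the interview clock appears (the assessment schedule and the fasting draws):

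- Time visit 2 from the end of the man's 16-week walk programme, in a short stated window after the week-16 walk.
- Time visit 3 at three months after that, as the Background already describes.
- Schedule the baseline interview and blood draw within a short stated window before the group's first walk.

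A repeat baseline for a man who has waited longer is optional and not needed for this correction.

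The cost is a wording amendment, visits scheduled by walking group, and longer calendar follow-up for early recruits. No additional participants are needed.

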We will use a multi-faceted recruitment strategy that has been successfully implemented at the University of Miami/Jackson Memorial Medical Center (UM/JMMC) Adult HIV Outpatient Clinic consisting of advertisements, informing clinic staff of the study, and direct recruitment by the CHW. The CHW (a UM employee who is to be determined) will coordinate with the Clinical Sciences Core and the Behavioral/Social Science & Community Outreach Core of the Miami Center for AIDS Research (CFAR). The CFAR Clinical Sciences Core (Core C) provides state-of-the-art facilities for implementation of clinical studies, clinical research and services including sample and data collection. The location of Core C next to the Special Immunology clinics allows recruiting participants in an efficient manner on the same day of clinic visit. Behavioral/ Social Science & Community Outreach Core (Core E) provides CFAR investigators with consultation and resources to expand behavioral clinical studies. HIV-infected patients receive

IRB Study Number: 20181032

Version 8, Date: 07/16/2021

primary care from their HIV care providers at the UM/JMMC Adult HIV Outpatient Clinic. The CHW will work with Clinic staff to educate them about the study as well as the inclusion/exclusion criteria. Clinic staff will identify potential participants through the electronic medical records and matched with the weekly clinic census. Clinic staff will introduce the CHW to potential participants during their regularly scheduled HIV care visit at the Clinic. The CHW will describe the study to the potential participant. If he is interested, then the CHW will go over the consent form. After the participant has signed the consent form, he will be asked to sign HIPAA Research Authorization – Form B, which authorizes study personnel to access the participant's protected health information, specifically the cardiometabolic parameters of interest, HIV/AIDS status, and viral load. No other individually identifiable health information will be shared with study investigators.

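### Fasting is required for the 4- and 7-month blood samples but not at baseline, where laboratory values come from the medical record with no age limit; the listed analytes also cannot supply the promised HOMA

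*Combined protocol and SAP*

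**What the plan says.** All of the sampling text is in Section 8 (Procedures Involved) of the combined protocol and SAP.

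- Baseline draw: "Prior to starting the baseline assessments, blood draws will take place at the UM/JMMC Adult HIV Outpatient Clinic". No fasting condition and no analytes are attached to it.
- Baseline values, in the next sentence: "Study staff will obtain initial HDL-C, LDL-C, triglycerides, insulin, and HbA1c levels via review of the electronic medical records".
- Follow-up: "At 4 and 7 months after the initial interview, fasting blood samples will be drawn via venipuncture and stored at 4°C until analysis". This is the only place in the document where fasting is mentioned.
- Derived index, directly after the follow-up draws: "HOMA will be calculated, providing a measure of insulin resistance".
- Under Assessment Measures, current medications and waist circumference are listed first, followed by "total cholesterol, HDL-C, LDL-C, triglycerides, blood pressure, and HbA1c, will be used to measure cardiometabolic risk".
- At the start of the section, participants are to be assessed at all three time points "on measures of cardiometabolic risk factors (waist circumference, dyslipidemia, hypertension, and glucose), psychosocial functioning, and health-related quality of life".

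Section 10 (Data Management) describes an ANOVA of the change from baseline to post-intervention for every outcome measure, then a repeated-measures ANOVA. The covariates are age, SES, years of education and medication changes. Section 6 sets enrolment at 18. After baseline, all participants enter HOLA.

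**The concern.** The plan states one sampling condition for follow-up and leaves it open for baseline. In a randomized comparison, a baseline-only difference in sampling would tend to affect both arms alike. Here there is one group, so nothing offsets it, and any systematic difference between baseline and follow-up samples is carried into the estimated change.

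The fasting question bears on triglycerides, insulin and HOMA. For HbA1c, only the age of the record value is at issue. Waist, blood pressure, the psychosocial scales, quality of life and the Aim 1 feasibility criteria are untouched.

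There is also a gap in the measurement list. HOMA is computed from fasting glucose and fasting insulin, and the two lists in Section 8 do not provide that pair at any visit. Exploring change in glucose and the other cardiometabolic factors is a stated aim (Aim 3), so the plan should say what is assayed and when.

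**Working it through.** The plan gives no figure to reproduce and no offset size. The check sets the statements side by side.

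**1. Sampling conditions.** Fasting is required at 4 and 7 months and not stated at baseline. There are two ways to read the baseline sentences:
- The record holds the results of the pre-baseline clinic draw. Timing is then settled, but that draw has no fasting requirement.
- The record values are routine-care results. Fasting state and age are then both open.

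Fasting state at baseline is therefore unspecified under either reading. The age of the value is unspecified only under the second.

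**2. Effect on the contrasts.** Let the comparable fasting values be Y0, Y4 and Y7, and let the recorded baseline be Y0 + d, where d is the mean offset due to fasting state or timing.
- Baseline to 4 months: Y4 − (Y0 + d) = (Y4 − Y0) − d
- Baseline to 7 months: Y7 − (Y0 + d) = (Y7 − Y0) − d
- 4 to 7 months: Y7 − Y4, with no d

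Two of the three pairwise contrasts carry the offset in full. One of these, baseline to post-intervention, is the change Section 10 names. The planned covariates include neither fasting state nor sample date, so they are not designed to remove d. The documents give neither the size nor the sign of d.

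**3. Analyte lists.**

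| Analyte | Baseline record list | Assessment Measures list |
|---|---|---|
| HDL-C | yes | yes |
| LDL-C | yes | yes |
| Triglycerides | yes | yes |
| HbA1c | yes | yes |
| Insulin | yes | no |
| Total cholesterol | no | yes |
| Glucose | no | no |

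Each list has 5 analytes and 4 are shared, so the union is 5 + 5 − 4 = 6. Glucose makes 7. HbA1c could stand for the glucose domain, but it cannot supply HOMA.

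**The case against.** The best defence is that the two baseline sentences belong together: the clinic draws the blood and staff read the results from the record. Section 19 (Setting) places all blood draws at that clinic. This is the more natural reading, and on it the age of the value is largely not a problem. It still leaves the baseline draw without a fasting requirement.

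A reader might go further and infer that baseline values are old, unfasted routine results. Section 7 says the core's location "allows recruiting participants in an efficient manner on the same day of clinic visit", and "Clinic staff will introduce the CHW to potential participants during their regularly scheduled HIV care visit at the Clinic". That is weak support. It describes same-day recruitment, not same-day sampling, and Section 8 adds a second route by telephone through a registry. An unfasted baseline is possible under the plan but not shown.

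A reader might also infer that glucose will not be assayed. The documents do not support this. Glucose is named as assessed at all three time points, the Assessment Measures list is not tied to a visit and not clearly exhaustive, and the promise of HOMA implies that glucose and insulin will be assayed at follow-up. Nor is a biased HOMA change established: the HOMA sentence follows the 4- and 7-month draws, and without baseline glucose there is no baseline HOMA to bias.

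A difference in laboratory between visits might be suspected too, but none is documented; the assay laboratory is not stated for follow-up either.

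Finally, this is an 18-man pilot, expressly not powered for hypothesis testing, and these outcomes are exploratory. That limits the consequence. It does not remove it, because exploring these changes is a stated aim.

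**Conclusion.** The point holds as a gap that should be fixed, with consequences confined to exploratory Aim 3 laboratory outcomes. The plan sets a fasting condition at follow-up that it does not set at baseline, and it places no age limit on record values. Followed as written, it can produce apparent change in triglycerides and insulin that has nothing to do with HOLA, and in HOMA if a baseline HOMA is calculated.

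The size is unknown. The documents give no offset and no count of men affected, and the offset is zero if the baseline draws are in practice fasting and current. It would be going too far to say that any observed improvement is spurious, or to state its direction.

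The HOMA gap is one of specification: the listed analytes cannot supply the index, although the promise to calculate it implies the follow-up assays. This rests on HOMA needing glucose and insulin from a fasting sample.

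**What to change.** State in Section 8 that:

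- Baseline laboratory values come from the pre-baseline clinic draw, taken fasting.
- The same panel is assayed at baseline, 4 and 7 months: total cholesterol, HDL-C, LDL-C, triglycerides, glucose, insulin and HbA1c.
- HOMA is calculated only where fasting glucose and insulin come from the same sample.
- Older record values are used for eligibility only.

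For men already enrolled, record the date and fasting status of the baseline sample. Repeat the triglyceride, insulin and HOMA changes without non-fasting or undated baselines as a sensitivity analysis.

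The cost is a fasting instruction, occasional rescheduling of a man who arrives unfasted, and added baseline assays for up to 18 men. If the record already holds the planned draw, glucose and total cholesterol are added: 18 × 2 = 36 results. If the record values are routine-care results, the full panel is needed: up to 18 × 7 = 126. The sensitivity analysis will run on a smaller sample, so it can indicate a problem but not settle it.

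As a separate minor drafting point, Section 8 stores samples at 4°C and Section 9 (Data and Specimen Banking) at -80 °C, each until analysis. These may be successive steps, but the two statements should be reconciled.
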